**NCT04800432**

**Last updated:** 11/19/2021

Study Title: ADAPT+: Optimizing an Intervention to Promote Healthy Behaviors in Rural, Latino Youth with Obesity and their Parents, using Mindfulness Strategies.

Proposal # #Pro00039979

PI: [name].

Dept. of Child and Family Studies

Guidelines for studies meeting the criteria for expedited or full Board review:

A. Overview:

1. Rationale for the study, area of current scientific concern and why the research is needed;

Rates of obesity among Latino youth is increasing exponentially. It is estimated that unless this trend is reversed, 90% of US-born children of Mexican immigrants will be of overweight or obese status by 2030, particularly those living in rural communities. With a rise in obesity, Latino youth are at increased risk for metabolic syndrome, type 2 diabetes, cardiovascular disease and cancer. Lifestyle interventions have predominantly depended on education and cognitive-behavioral strategies to improve diet and physical activity (PA), with parent- focused interventions showing the most consistent success for youth. Still, these studies often produce only modest and short-term results. The link between parent stress and offspring obesity has been shown, yet the role of parent stress on obesity has not been well addressed in interventions for reducing obesity in Latino youth. Evidence implicates stress in disordered eating and obesity and parent stress relates to risk factors for childhood obesity.

Mindfulness-based programs are successfully delivered to low-income, minority, public school students; however, few studies target Latino families.

2. Living in a rural community compounds the health care disparity of Latino youth and obesity.

Most Latinos in Florida (outside of Miami) live in rural areas and work as migrant farmworkers. Latino youth living in rural areas are 25% more likely to have overweight/obesity than Latinos in urban areas. Compared with Latinos living in urban areas, Latinos in rural areas typically consume more meals with friends and relatives outside the home, making food choices more difficult. Lack of access to affordable, healthy foods; few community resources; acculturation-related dietary changes (e.g., eating more processed and fast foods) and poverty are key contributing factors to obesity. Children in households living below the poverty line have 243% higher odds of developing childhood obesity than children living above the poverty threshold. Latino rural communities have been largely ignored despite the rising economic, social, and personal burden of obesity, including medical care costs.

3. Link between Latino parent stress and offspring obesity.

A growing body of evidence implicates stress in obesity, especially related to food choices and preferences. An American Psychological Association survey reported 39% of adults overeat or increase intake of calorie-dense foods in response to stress. Moreover, inability to maintain improvements in healthy lifestyle behaviors is linked with psychological distress in individuals with obesity. In youth, chronic stress has been linked with larger waist circumference and BMI. Latino families are especially subject to specific and burdensome stressors (e.g. economic hardship and fear of family member deportation) that may predispose them to behaviors that increase obesity. The large scale “SOL” investigation of Latino youth and their caregivers (n=473; children aged 8–16 years) found the incidence of youth obesity

increased substantially with the number of caregiver stressors. Long work hours, common among migrant worker families, can reduce parent involvement, including uninvolved feeding style, which can increase risk of obesity in youths. Specifically, parent stress is associated with decreased physical activity (PA), overeating and higher body weight in both children and parents. Given the literature that highlights the importance of focusing on parents in changing eating, PA and other health behaviors in youth, targeting parent stress to impact these behaviors may be key. However, there is a lack of culturally competent, evidence-based, interventions to address stress and its concomitant relation with the urgent public health issue of overweight/obesity among rural Latino youth.

#### 4. Critical barriers to progress in the field:

Most obesity interventions for Latino youth report mixed findings, are small in scope and exploratory and fail to incorporate key factors important for Latinos living in rural communities. For example, community-based interventions promote better ‘buy-in’ from Latino families, particularly utilization of promotoras (community health workers), yet most available studies have not delivered interventions in a community setting. Moreover, the “state of the obesity intervention field” suggests that interventions that are parent-focused, but also involve the entire family, show the most promise. This is particularly the case in Latino families because of the strong commitment to the family system (“familismo”), yet most extant studies involving Latinos do not include children. The majority of studies also have lacked: rigorous experimental methodology, manualized treatment programs that measure both physical activity (PA) and eating behaviors, culturally appropriate strategies, and longitudinal follow-up assessments. To date, obesity interventions with Latinos have also lacked sufficient attention to barriers to success, including acculturation considerations which include, dietary changes such as, using larger quantities of sodium, oils, and sugars; consuming an excess of sugar-sweetened beverages and fast food; and having a suboptimal consumption of fruits and vegetables. We argue here that mixed results of interventions may also be due to their failure to successfully address multi-faceted psychosocial risk factors, such as parent stress. Multifaceted approaches must be taken into consideration in designing intervention strategies to increase the effectiveness and sustainability of health behavior changes for migrant Latino families. In response to these barriers to success, our refined intervention will focus not only on acculturation considerations of dietary changes, PA, but also parent stress within the family.

#### The research questions, objectives and purpose:

The purpose of this study is to refine and optimize an obesity intervention with rural underserved Latino children and their parents that combines a standard family-based behavioral approach, the “gold standard” for pediatric obesity treatment, with a mindfulness approach focusing on stress reduction (now ADAPT+).

Aim 1: Refinement of and optimization of ADAPT+ (ADAPT + mindfulness parent stress reduction combination) manual and intervention.

We assess acceptability of ADAPT and the integration of mindful parenting stress reduction (ADAPT+) to increase healthy lifestyle behaviors consistent with the needs of Latinos living in rural communities. We will conduct a series of focus groups: 1) with our community health facilitators/promotoras. Promotoras are community members who have been acculturated in the US but retain credibility with the target population. 2) a series of focus groups with parents

of children (8-12 years old) with obesity to obtain feedback and to refine each of our 6 integrated sessions and evaluate optimization of ADAPT+ sessions.

Aim 2: A small, randomized feasibility and acceptability study (ADAPT+ vs. Enhanced Usual Care comparison/EUC).

Aim 2 will be conducted in two rural communities. This aim evaluates: study sample selection and recruitment, willingness to be randomized and retention; fidelity of intervention administration, intervention adherence, and further refinement of manuals, feasibility of data collection procedures, including collecting a battery of measures from parents and children,\* data quality and sensitivity of our measures to our intervention effects over time – from baseline, post-intervention (after 6 sessions), and then 3-months post-intervention. We anticipate that compared to EUC, parent-child dyads in ADAPT+ will have a lower attrition rate and will report greater program satisfaction, and our eating, PA and stress-related measures will be sensitive to the intervention.

The foundation/basis of the proposed study is that parent stress reduction via mindfulness strategies will increase access to mind-body practices that may support and promote implementation of healthy behaviors in both parents and children. This project will provide crucial data to inform a larger trial application to test whether adding mindfulness techniques increases the ability of parents to assist their children in keeping healthy behaviors related to eating and physical activity. This programmatic research advances the understanding of mechanisms of behavioral interventions for improving health and well-being using mind-body practices.

**B. \*Measures to be used:**

Baseline, post-intervention and 3-months follow-up:

**Child BMI:** Height (to the nearest 1/4 inch) using a stadiometer and weight (to the nearest 1/4 pound) using a medical balance beam scale will be measured by study staff. The CDC Growth Charts will be used to obtain the continuous child BMI z score for gender and age. Our nurse scholar and RNP co-I completes all the anthropometric assessments.

**Child Waist-to-Hip Ratio:** Circumference of the hip (girth of hips above the gluteal fold) and waist (narrowest part of torso above the umbilicus and below the xiphoid process) will be measured by study staff using an anthropometric measuring tape and used to calculate continuous Waist-to-Hip Ratio. Our nurse scholar and RNP co-I completes all the anthropometric assessments.

**Resting Blood pressure for children:** assessed in triplicate using an automated blood pressure analyzer, with the participant in a seated position. Elevated BP is defined as either systolic or diastolic BP >90th%ile for age, sex, and height. Our nurse scholar and RNP co-I completes all the anthropometric assessments.

**Child Food and Physical Activity Questionnaire:** The questionnaire consists of 11 questions on food and physical activity behaviors for youth participants in the study. This was adapted from the USDA Youth Expanded Food and Nutrition Education Program (EFNEP) evaluation tool, the EFNEP 3rd-5th Grade Survey, which was designed and tested by Purdue University Extension Program.

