1. Latino families with a child between the ages of 8 and 12; Note: pre-adolescents are targeted as this is a developmentally critical age group in terms of developing health-behavior skills and is an age group identified as in need of further study in the Latino population. 2. Child with a BMI %ile of 85 or higher; and 3. The target parent is at least 18 years old, is the main meal preparer, speaks and reads Spanish at a minimum of a 4th grade reading level (able to follow basic instructions in Spanish), and able to perform simple physical exercises. Although both parents and/or other caregivers can participate in the group, only data from the primary parent (main meal preparer) will be used for analyses. The parent is ineligible if he/she is non-ambulatory, is pregnant, or has a medical condition that may be negatively impacted by PA. A child who has a medical/developmental condition that precludes weight loss using conventional diet and PA methods or has been on antibiotics or steroids in the previous three months is also ineligible.

E. The expected results of the research, such as reports, papers, and contributions to theory;

We posit that mindfulness can improve intervention engagement (increasing receptiveness), which are demonstrated critical barriers to Latino families participating in childhood obesity interventions, by simultaneously reducing stress and enhancing the learning process around eating and PA. ADAPT plus mindfulness parent stress reduction to increase healthy eating and PA lifestyle behaviors in both parents and their children.

F. Name of the Principal Investigator and Faculty Advisor if applicable;

[name]

G. Any potential risks to the subjects;

This research is considered to be minimal risk. That means that the risks associated with this study are the same as what the participant would face every day. There are no known additional risks to those who take part in this study.

H. Any experimental procedures or interventions that will be implemented;

The study will assess acceptability of the integration of mindfulness parenting stress reduction into Adaptando Dieta y Acción Para Todos (ADAPT) to increase healthy lifestyle behaviors by: conducting a series of focus groups with our community health facilitators/ promotoras and parents of children (8-12 years old) with obesity to obtain feedback about and refine each of our 6 integrated sessions and evaluate optimization of ADAPT+ sessions.

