#### K. Statistical Analysis Plan

Preliminary evaluation of participants' response to the interventions will be examined using quantitative data. While evaluation of outcomes is more appropriate for a fully-powered R01, we will examine variance and effect sizes of key outcomes from pre- to post-intervention, as well as post-intervention to 3-month follow-up using non-parametric tests and confidence intervals. The randomized trial is powered to detect an average estimated effect size equivalent to Cohen's  $d$  of 0.50 with the minimum sample size of 96 participants (i.e., 48 children, 48 parents). Analyses will explore potential patterns related to attrition. Every effort will be made to collect follow-up data from all participants, regardless of whether they completed the intervention.

L. Research references:

3. Lichter DT. Immigration and the New Racial Diversity in Rural America. *Rural Sociol*. 2012;77(1):3-35.
5. Tuñón-Pablos E, J D. Risk Factors for Overweight and Obesity among Mexican Children in New York. *International Journal of Population Research*. 2016.

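### Child weight change is scored only as a CDC-chart BMI z in a sample with no upper BMI limit, so change in the heaviest children may be under-registered; an unflattened BMI measure could be added at little cost

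*Combined protocol and SAP*

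**What the plan says.** Section B (Measures) has child height and weight taken by study staff at three times: "Baseline, post-intervention and 3-months follow-up". One score is specified from them: "The CDC Growth Charts will be used to obtain the continuous child BMI z score for gender and age". The only other child adiposity measure is based on circumferences, which are "used to calculate continuous Waist-to-Hip Ratio". For parents, by contrast, the score is plain continuous BMI.

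Section D sets the child criteria as "Latino families with a child between the ages of 8 and 12" and "Child with a BMI %ile of 85 or higher". The child exclusions cover recent antibiotics or steroids and conditions that would prevent weight loss by ordinary means ("A child who has a medical/developmental condition that precludes weight loss using conventional diet and PA methods"). None is based on BMI, so there is a floor and no ceiling.

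Aim 2 lists, among the things to be evaluated, "data quality and sensitivity of our measures to our intervention effects over time". Section K says that "we will examine variance and effect sizes of key outcomes from pre- to post-intervention". It names no weight metric and no primary outcome. The documents do not discuss how BMI z behaves at high BMI and give neither chart parameters nor an expected BMI distribution.

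**The concern.** A growth-chart z is built to place a child within a reference population. It need not respond evenly to change far out in the tail. If the reference is right-skewed and the z removes that skewness, successive BMI increments at the top of the scale are worth less and less z. Two children who each lose the same percentage of BMI would then be credited differently, and the heavier child would be credited less.

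This trial recruits only from the upper tail. A flattened scale could make child BMI look less responsive than it is, and part of the spread in z change would reflect where children started. That bears on the Aim 2 question about sensitivity of measures. It would also bear on the larger application if child BMI z were used to plan it.

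**Working it through.** The plan gives no figure for this effect, so there is none to reproduce. The effect size of 0.50 in section K does not enter the calculation.

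**Inputs from the documents.** CDC-chart BMI z as the only weight score (section B); entry at the 85th percentile or above with no upper limit (section D); three cohorts per arm of at least 8 pairs, so at least 24 children per arm (section C, Sample size).

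**Assumptions.** The chart z is an LMS score with median M, coefficient of variation S and skewness L. L is varied from 0 to -3. P95 denotes the 95th-percentile BMI for age and sex.

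**Formula.** z = ((BMI/M)^L - 1)/(L x S). For L < 0, z cannot exceed -1/(L x S). With L from -2 to -3 and S from 0.11 to 0.15, that ceiling runs from 1/(2 x 0.11) = 4.5 down to 1/(3 x 0.15) = 2.2.

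**Credit for a percentage change.** If BMI goes from B to kB, the fall in z is (B/M)^L x (1 - k^L)/(L x S). Take one child at P95 and another of the same age and sex at f x P95. For the same k, the ratio of their z changes is f^L. M, S and k cancel, so only L matters.

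| L | Loss at 1.2 x P95 (1 - 1.2^L) | Loss at 1.4 x P95 (1 - 1.4^L) |
|---|---|---|
| 0 | 0% | 0% |
| -1 | 17% | 29% |
| -1.5 | 24% | 40% |
| -2 | 31% | 49% |
| -2.5 | 37% | 57% |
| -3 | 42% | 64% |

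A loss of one half at 1.4 x P95 requires L = -ln 2/ln 1.4 = -2.06 or lower.

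**Worked example.** Take L = -2.5, M = 16.6, S = 0.125. The ceiling is 1/(2.5 x 0.125) = 3.20, the 85th percentile is 19.4 and P95 is 22.2. A 4% fall in BMI is worth 0.167 z at P95, 0.106 at 1.2 x P95 and 0.072 at 1.4 x P95. The ratio 0.072/0.167 = 0.43 agrees with 1.4^-2.5.

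**Choice of scale.** Per kg/m2 rather than per percent, the slope ratio is f^(L-1), which is steeper. At L = -2 and 1.4 x P95 it is 1.4^-3 = 0.36, a 64% loss instead of 49%. Any figure therefore needs its scale and reference point stated.

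**Effect on an arm mean.** Suppose all 24 children in an arm have the same percentage change. Replacing one child at P95 by one at 1.4 x P95 lowers the arm's mean z change by (49% to 64%)/24, or about 2% to 3%, for L of -2 to -3. The total depends on how many such children enrol, and the documents do not say.

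**The alternative metric.** BMI as a percentage of P95 is linear in BMI. A 4% fall scores 0.04 x 100 = 4.0 points at P95 and 0.04 x 140 = 5.6 points at 1.4 x P95. It is not flattened, but it weights an equal relative change by the baseline level, 1.4 times more at 1.4 x P95. On the log scale the same fall is ln 0.96 = -0.041 at every starting BMI, before any shift in P95 with age.

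**The case against.** The strongest reply is that this is a small feasibility and acceptability study. No outcome is named as primary, and section K itself says that outcome evaluation belongs in a fully powered trial. The measures that Aim 2 expects to respond are those for eating, physical activity and stress, not BMI. Height and weight are recorded at every visit, so any BMI metric can be derived later and nothing is lost. Entry begins at overweight, and many children may lie near the 85th to 95th percentiles, where flattening is modest. All of this stands, and it lowers the weight of the point. It does not remove it, because sensitivity of the measures is an Aim 2 question and section K will report variances and effect sizes.

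A reader might infer that the heaviest children's change is cut by half or more. The documents do not support that as a general statement. Relative to the 95th percentile it is not reached at 1.2 times that value for any L in the range examined. At 1.4 times it needs L of about -2.06 or lower, and nothing shows that children that heavy will enrol. A reader might also infer that a distorted effect size will be passed to the efficacy trial. No section says that child BMI z will size that trial. Nor is percent of the 95th percentile a complete cure, since it carries a smaller weighting by baseline in the opposite direction.

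**Conclusion.** The point holds in a limited form. From the documents alone: CDC-chart BMI z is the only score specified for child weight, waist-to-hip ratio is the only other child adiposity measure, and the sample is the upper tail of the reference with no ceiling. The flattening follows algebraically if the chart z is an LMS score with negative L. That form and the value of L are assumptions, and if L is near 0 there is no loss per percentage change. The size for an individual child is as tabulated. The size for an arm mean cannot be fixed without the enrolled BMI distribution. Severity: CONSIDER.

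**What to change.** In section B, add BMI as a percentage of the age- and sex-specific CDC 95th percentile at each visit, derived from the height and weight already taken, and state how the BMI z is computed. In section K, report the change, variance and effect size of the new measure alongside those of BMI z, and state that BMI z alone will not be used to judge sensitivity or to inform the larger trial. Analysing the new measure as relative change, on the log scale, removes its weighting by baseline.

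The cost is a sentence or two in each section and one more derived outcome to report. No new measurement is required, and keeping BMI z preserves comparison with other studies that use it.

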## Protocol, Version #10

Parent BMI: Height (to the nearest 1/4 inch) using a stadiometer and weight (to the nearest 1/4 pound) using a medical balance beam scale will be measured by the study staff and used to calculate continuous adult BMI score. Our nurse scholar and RNP co-I completes all the anthropometric assessments.

Parent Waist-to-Hip Ratio: Circumference of the hip (girth of hips above the gluteal fold) and waist (narrowest part of torso above the umbilicus and below the xiphoid process) will be measured by the study staff using an anthropometric measuring tape and used to calculate continuous Waist-to-Hip Ratio. Our nurse scholar and RNP co-I completes all the anthropometric assessments.

Resting Blood pressure for Parents: assessed in triplicate using an automated blood pressure analyzer, with the participant in a seated position. Elevated BP is defined as either systolic or diastolic BP >90th%ile for age, sex, and height.

Our nurse scholar and RNP co-I completes all the anthropometric assessments.

Dietary Habits: The Latino Dietary Behaviors Questionnaire: This 13-item self-report survey of dietary habits (in Spanish) assesses 4 areas of eating behavior -- healthy dietary changes; types of drinks consumed, number of meals per day and fat consumption. The LDBQ factor structure is relatively stable over time, and correlates significantly with the 24-HR dietary recall measure and clinical variables such as BMI, and behavioral indicators of diet. It is specifically designed for low literacy populations and has been validated in large samples of ethnically diverse Spanish speaking samples.

Perceived Stress Scale (PSS): Parents complete the 14 item self-report scale that asks participants about their feelings in the past month. The PSS measures psychological stress associated with sex, age, education, income, employment status, and a number of other demographics.

Mindful Eating Questionnaire (MEQ): Parents will complete the Recognize Subscale of the MEQ. The MEQ is a 28-item scale developed to measure the construct of mindful eating, a nonjudgmental awareness of the physical and emotional sensations associated with eating. The Recognize subscale has 9 items and is designed to assess an individual's ability to stop eating when full.

At Baseline Only: Parents will complete the *Stephenson Multigroup Acculturation Scale (SMAS)*, and a short demographic questionnaire.

Exit survey: At the end of the intervention, after 6-weeks, parents in both conditions will complete a brief exit survey to assess their overall satisfaction with the intervention and their opinion of its impact on their knowledge of childhood obesity and healthy eating, physical activity behaviors, mindfulness parent stress reduction approaches, as well as how well the content fit their needs and cultural values. For example, what they liked/disliked about the intervention, what additional information they might have wanted, the extent to which they felt they increased their understanding of healthy lifestyle behaviors and stress reduction strategies.

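### Parent BMI has no fixed-height rule, so re-measuring adult height at each visit would add avoidable noise to parent BMI change (minor)

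*Combined protocol and SAP*

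**What the plan says.** Section B (Measures to be used) opens its list with the heading "Baseline, post-intervention and 3-months follow-up". Under Parent BMI it specifies "Height (to the nearest 1/4 inch) using a stadiometer and weight (to the nearest 1/4 pound) using a medical balance beam scale", and says that these readings "will be measured by the study staff and used to calculate continuous adult BMI score". Within the list, only the acculturation scale and the demographic questionnaire are set apart as baseline-only. Nothing says which visit's height enters which BMI, whether baseline height is carried forward, or whether repeat heights are averaged. The same section assigns all anthropometric assessments to one nurse co-investigator role, although it also names study staff.

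The eligibility criteria (section D) state: "The target parent is at least 18 years old".

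Section K (Statistical Analysis Plan) will "examine variance and effect sizes of key outcomes from pre- to post-intervention", and likewise from post-intervention to the 3-month follow-up. It does not list the key outcomes. Aim 2 in section A makes data quality and the measures' sensitivity to change over time objects of the pilot.

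**The concern.** BMI is weight divided by height squared. A parent's true height does not move during six weeks of sessions and three months of follow-up, so a change in recorded height carries no information. If each visit's BMI uses that visit's height, the reading error of two heights enters every parent BMI change. It is magnified by about 2 × BMI / height per unit of height.

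What is at stake is precision. The pilot is meant to pass variances and effect sizes on to a larger trial. Avoidable error makes the variance of parent BMI change too large and its standardised effect too small.

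**Working it through.** **Inputs from the document.** Height step 0.25 in (0.635 cm); weight step 0.25 lb (0.1134 kg); three visits; parents aged 18 or over; minimum 48 parents. The plan states no figure for this point, so there is none to reproduce.

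**Inputs assumed, because the document gives none.** A parent of 62 in (1.5748 m) with BMI 30; a wider range of 58 to 70 in and 120 to 250 lb; a reading-error SD of 0.2 to 0.5 cm per height; an SD of true weight change of 1.5 to 3 kg.

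**1. One height step.** At fixed weight the change in BMI is BMI × [1 − (H/(H + 0.25))²].
- 30 × [1 − (62/62.25)²] = 0.240 BMI units.
- In weight terms: 0.240 × 1.5748² = 0.60 kg = 1.31 lb.
- A 0.25-lb weight step: 0.1134 / 1.5748² = 0.046 BMI units. In BMI terms the height step is about five times coarser (0.240 / 0.046 = 5.2).

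**2. Range over parent size.** The weight equivalent is W × [1 − (H/(H + 0.25))²].

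| Height (in) | Weight (lb) | One step (lb) |
|---|---|---|
| 70 | 120 | 0.85 |
| 62 | 120 | 0.96 |
| 62 | 160 | 1.28 |
| 62 | 200 | 1.60 |
| 58 | 250 | 2.14 |

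**3. Noise between two visits.** Simulation of adults with BMI 30 and constant true height between 150 and 165 cm, with an independent reading error at each visit. "Step" in the table means readings rounded to 0.635 cm. The last column is the squared ratio of the two SDs.

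| Reading-error SD (cm) | Parents with a false height change | False BMI-change SD, with step | Same, unrounded | Share of noise variance from reading error |
|---|---|---|---|---|
| 0.2 | 35% | 0.146 | 0.108 | 54% |
| 0.3 | 49% | 0.190 | 0.162 | 73% |
| 0.5 | 66% | 0.287 | 0.270 | 88% |

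With no reading error, the same height rounds to the same value at both visits and the added noise is zero.

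**4. Effect on variance and standardised effect.** The assumed weight-change SD converts to 1.5 / 1.5748² = 0.60 up to 3 / 1.5748² = 1.21 BMI units. Relative rise in variance = (noise SD / true SD)².
- Smallest: (0.146 / 1.21)² = 1.5%.
- Largest: (0.287 / 0.60)² = 23%.
- A true d of 0.50 would appear as 0.50 / √1.015 = 0.496 down to 0.50 / √1.23 = 0.45.

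**5. Sensitivity to the assumptions.** For a parent of 62 in and 160 lb with a reading-error SD of 0.1 to 0.3 in, variance rises by 1–8% if the SD of true weight change is 8 lb, 2–15% at 6 lb, 5–33% at 4 lb and 21–129% at 2 lb. The problem is large only where true weight change varies little.

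**6. With one height per parent.** The height contribution to BMI change disappears. What remains is a constant scale error in each parent's change, at most about 2 × 0.5 / 157.5 = 0.6% per SD of reading error.

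**The case against.** The other side has four good points.

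- The document does not say outright that each BMI uses that visit's height. This is inferred from the heading over the list. It stands as a limit: the fault is an unspecified rule whose natural reading is the poorer method.
- A reader might infer that the 1/4-inch step itself creates the noise, or that 1.3 lb describes this trial's parents. Neither is supported. Rounding alone adds nothing to parent change, and 54% to 88% of the simulated noise variance is repeat-reading error. The 1.3 lb is a worked example for an assumed parent. Having one role take the measurements should also hold down between-observer error, though within-observer error remains.
- A reader might infer a biased treatment comparison. Nothing in the documents suggests that height error differs by arm; if it is equal, the mean difference is unbiased.
- The consequence is modest. Parent BMI is not named a key outcome, and Aim 2 expects sensitivity in the eating, activity and stress measures. Section K itself regards outcome evaluation as better suited to a fully powered trial. With about 24 parents per arm (assuming the 48 split equally), a sample variance has a relative standard error of about √(2/23) = 29%, which exceeds the inflation in step 4.

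It is also tempting to extend the point to children and ask for finer height readings. The documents do not support that. Children grow, so their height must be re-measured. Their outcome is a BMI z score, on which no effect has been quantified, and nothing shows that the stadiometer can be read more finely than 1/4 inch.

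These points reduce the size of the concern. They do not supply the missing rule.

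**Conclusion.** The point holds, for parents only and as a minor one. The mechanism is certain once a fresh height is used at each visit, and that is how the list of measures most naturally reads. The effect is lost precision: roughly 1.5% to 23% more variance in parent BMI change, and a d of 0.50 seen as 0.45 to 0.50. Those figures rest wholly on the assumed parent size, reading error and SD of change. The loss is recoverable, because height and weight are both recorded and parent BMI can be recomputed. It is still worth correcting, since the better method is free and the variances are meant to inform a later trial.

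**What to change.** Add one sentence to section B under Parent BMI: parent BMI at every visit is calculated from a single height per parent, either the baseline height or the mean of the heights taken, so that change in parent BMI reflects change in weight only. Choose one of the two before analysis. The baseline height has the advantage of not depending on attendance at later visits.

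The cost is that sentence. It needs no extra visit, staff or procedure, and it can be applied at analysis to data already collected. No change to child height measurement is proposed.
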